### **6.6.2 Statistical Power and Sample Size Considerations**

We have powered the study to detect a 0.67 difference in weight-for-age z-scores between the observational and future intervention groups. To detect this difference with 90% power and a 5% Type I error rate, 276 participants are required. This includes an anticipated 30% loss to dropout. This study is also powered on food to soothe a distressed child and uses nominal power = 0.8 and alpha = 0.05. If we assume that we can change 15% of mothers in the future treatment group to reduce their use of food to soothe as compared to mothers in the observational study, assume a constant variance of 1 and a retention rate of 67% during the study period, we will need to recruit 300 pediatric participants. We have experienced a 31-33% drop-out rate in previous studies of mother/guardian-infant dyads for longer than 3 months duration, and so assume a similar drop-out for this study.

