This prospective study will have two sequential phases 1) observational study; 2) interventional randomized controlled trial. Mother/guardian-infant pairs of infants that have a Geisinger primary care provider in the Geisinger Pediatric Service Line and who participate or are eligible and plan to participate in WIC will be enrolled in a single phase of the study. The purpose of the observational phase is to obtain a baseline of participant measures with usual, uncoordinated care in the Pediatric Service Line and WIC. The purpose of the randomized controlled trial is to evaluate the differences between groups that experience coordinated versus uncoordinated care. Two phases are necessary because the Geisinger Pediatric Service Line (PSL) implements a standard of care, known as Early Healthy Living/Lifestyles (EHL) screening, that is not implemented nationally and potentially limits the generalizability of study findings. In prior studies (IRB# 2012-0363), the EHL screening tool has been evaluated. The EHL screening is undergoing modifications to improve health literacy, numeracy, and alignment with evidence-based recommendations. Thus, the PSL will temporarily turn off the EHL screening for these revisions and staff training, thus allowing for an observational phase of usual, uncoordinated care. The updated EHL screening tool (Attachment 1) will be made available as standard of care in the PSL when phase 2 begins [Note that this is a clinical screening tool and not a study questionnaire]. Mother/guardian-infant dyads in both groups of phase 2 will be exposed to the EHL screening but only one group will have coordinated care with WIC. Knowledge, behavior, and attitudes are expected to be more desirable among mother/guardian-infant pairs with coordinated care when compared to those receiving status quo. Additionally, infants with coordinated care are expected to have slower (as opposed to rapid and risky) weight gains in comparison to infants with uncoordinated care. Mothers/guardians are expected to indicate greater satisfaction with coordinated versus uncoordinated care.

---

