## 6 STUDY DESIGN

### 6.1 Description

This prospective study will have two sequential phases 1) observational study; 2) interventional randomized controlled trial. In phase 2, qualifying participants will be randomized 1:1 to receive either Treatment A or Treatment B.

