### 6.2 Study Population

#### 6.2.1 Approximate Number of Subjects

Approximately 715 Geisinger subjects will participate in this study, 15 mother/guardian-infant pairs will participate in the observational phase and a total of 350 mother/guardian-infant pairs will participate in the RCT phase. The study team has accounted for participant drop-out by planning to enroll 350 Geisinger subjects, recognizing that a to meet power calculations a total of 15 observational control dyads and 350 intervention/control dyads are needed. Mother/guardian-infant pairs of infants that have a Geisinger primary care provider in the Geisinger Pediatric Service Line and who participate or are eligible and plan to participate in WIC will be enrolled in a single phase of the study. Pregnant women who are eligible for or participate in WIC who also intend to have their newborn receive care from a Geisinger primary care provider in the Geisinger Pediatric Service Line will be enrolled in a single phase of the study.

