### Primary Endpoints

The primary endpoint will be excessive rapid weight gain, or weight-for-age z-scores, at post-intervention. The phase one observational study provides the naïve condition of weight-for-age z-scores that will be compared to treatment group in the randomized controlled trial. A 0.67 difference in weight-for-age z-scores represents the distance between major centile lines displayed on infant growth charts. This difference is clinically meaningful, and upward percentile crossing of this magnitude has been the operational definition for rapid weight gain.

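### The primary weight-for-age comparison is powered at 90% against a phase-one observational group of only 15 dyads, and no power statement covers the 1:1 randomised arms

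*Protocol*

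**What the plan says.** Section 6.6.2 defines the powered contrast: "We have powered the study to detect a 0.67 difference in weight-for-age z-scores between the observational and future intervention groups". It continues: "To detect this difference with 90% power and a 5% Type I error rate, 276 participants are required", a figure that already allows for 30% dropout. No SD is given for weight-for-age z-score. The second calculation there, on food to soothe, gives 300 and also compares treated mothers with those in the observational phase.

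Primary Endpoints (after 6.5.2) names the same contrast. Phase one supplies "weight-for-age z-scores that will be compared to treatment group in the randomized controlled trial".

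Section 6.2.1 plans the numbers: "Approximately 715 Geisinger subjects will participate in this study, 15 mother/guardian-infant pairs will participate in the observational phase", with 350 pairs in the trial phase. It says that "to meet power calculations a total of 15 observational control dyads and 350 intervention/control dyads are needed".

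The design sections point to a different comparison. Section 6.1: "In phase 2, qualifying participants will be randomized 1:1 to receive either Treatment A or Treatment B". Section 2: "The purpose of the randomized controlled trial is to evaluate the differences between groups that experience coordinated versus uncoordinated care".

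**The concern.** Two things do not fit together.

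First, the 0.67 difference and the 90% power are attached to phase-one observational versus randomised treatment. The observational group is 15 dyads, or about 10 if the planned dropout applies. With one group that small, the size of the other hardly matters, and 90% power looks out of reach for any ordinary SD.

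Second, the comparison that randomisation protects, treatment versus control within phase two, has no effect size, SD or power in the protocol.

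The observational contrast also carries bias that the randomised one does not. It comes from an earlier period. It draws on wider eligibility, because section 6.2.2 restricts phase two to Partners in Pediatrics patients and to WIC eligibility in Luzerne County. Its exposure to the EHL screening is unclear: section 2 says "the PSL will temporarily turn off the EHL screening for these revisions and staff training" to create the observational phase, but the phase-one table in 6.5.1 lists the EHL questionnaire at all four time points.

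Followed literally, the protocol would rest its primary endpoint on a small, non-randomised comparison. If it is left ambiguous, the comparator could be chosen after the data are seen.

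**Working it through.** **Inputs.** Difference 0.67, power 90%, type I error 5% (taken as two-sided) and 30% loss, all from 6.6.2. Group sizes are 15 observational dyads and 350 randomised (6.2.1), so 175 per arm at 1:1 (6.1). Loss of 31-33% is the past experience quoted in 6.6.2. The SD is an assumption, so a range is shown.

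**The protocol's 276.** For two equal groups, n per group = 2(1.960 + 1.282)² SD² / 0.67². At SD 1 this is 46.8, or 48 with the t-test. Then 96 / 0.70 = 137.1, about 138 dyads, which is 276 individuals. If 276 instead counts dyads, 276 × 0.70 = 193.2 are retained, 96.6 per group, and 90% power then implies an SD of 1.43. Both readings are inferences, and both assume equal groups: 69 or 138 observational dyads, not 15. Splitting 276 as 15 and 261 with 30% loss reaches 90% only at an SD of about 0.65.

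**Power at the planned sizes.** Noncentrality = 0.67 / [SD × √(1/n₁ + 1/n₂)].

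- With 30% loss, 10.5 vs 122.5: √(1/10.5 + 1/122.5) = 0.3216, so noncentrality at SD 1 is 2.08 and power is 54.3%.
- With no loss, 15 vs 175: √(1/15 + 1/175) = 0.2690, so noncentrality at SD 1 is 2.49 and power is 69.8%.

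| Assumed SD | 30% loss | No loss |
|---|---|---|
| 0.8 | 73% | 87% |
| 0.9 | 63% | 79% |
| 1.0 | 54% | 70% |
| 1.1 | 47% | 62% |
| 1.43 | 30% | 41% |

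The no-loss column is relevant because infant data come from health and WIC records (6.5), so an unreturned survey need not mean a missing weight.

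**Can a larger treatment group help?** No. At SD 1 an unlimited treatment group gives 58% (10.5 controls) or 74% (15 controls).

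**What would restore 90%?** An SD of 0.64 (30% loss) or 0.76 (no loss). Covariate adjustment with correlation r multiplies the SD by √(1 − r²), so at SD 1 this means r of about 0.77 or 0.64.

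| Assumed r, SD 1 | 30% loss | No loss |
|---|---|---|
| 0.5 | 67% | 82% |
| 0.7 | 83% | 93% |

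**The randomised arms.** 175 × 0.67 = 117.25 and 175 × 0.69 = 120.75 per arm. Power for 0.67 is over 99% at SD 1 and about 95% at SD 1.43. The difference detectable with 90% power is 0.425 SD and 0.419 SD respectively.

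**Counts.** 15 + 350 = 365 dyads, which is neither 276 nor 300. The stated 715 equals 15 + 2 × 350, whereas 365 pairs are 2 × 365 = 730 individuals.

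**The case against.** Primary Endpoints does not say that the observational contrast is the only or the confirmatory test. Section 2 gives the trial's purpose as coordinated versus uncoordinated care, section 4.1 tests against usual care, and section 6.6.1 models weight-for-age z-score by study group. On this view the randomised comparison is intended, and the trial is amply sized for it. That is a fair reading of the intent, and it is why the repair is cheap. It does not rescue the text: none of those sections makes the randomised contrast primary or gives it a power, and the two places that do define the comparison name the other one.

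The 54-70% range is also a simple case: one unadjusted time point and an SD the protocol does not give. Section 6.6.1 plans a mixed model with covariates, and weights are scheduled at four times, so the real precision may be better. This stands in part. With r = 0.7 and no loss, power passes 90%. But no correlation or variance reduction is stated, and 6.6.2 itself applies the 30% loss. The 90% is therefore unsupported, not impossible.

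The SD of 1.43 depends on one reading of 276. The other reading gives SD 1, which supports the main range. The 715 against 730 is a small discrepancy in an approximate figure, and matters only because it shows the counting unit is unclear. The difference in period follows from the sequential design, for which section 2 gives a generalisability reason. That reason supports having a phase-one group, but not making it the primary comparator with 15 infants.

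**Conclusion.** The concern holds, and the protocol is wrong as written. The stated 90% power belongs to a non-randomised comparison whose smaller group is 15 dyads. At an assumed SD of 1, unadjusted, that comparison has about 54% power with 30% loss and 70% without. No SD from 0.8 upward reaches 90% without adjustment. The claim in 6.2.1 that 15 + 350 dyads meet the power calculations has no counterpart in 6.6.2. The randomised comparison has no power statement, although its planned size gives over 99% at SD 1 and about 95% at SD 1.43.

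The fault lies in the choice of contrast and its justification, not in the size of the randomised trial. The power figures rest on the assumed SD and a two-sided 5% t-test. The mismatch between the sections needs no assumption.

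**What to change.** - **Primary Endpoints and 6.6.2:** name randomised treatment versus randomised control as the primary weight-for-age comparison. Keep the phase-one comparison as descriptive context.
- **6.6.2:** restate power for the randomised arms, giving the SD and saying whether counts are dyads or individuals. With 350 dyads and 31-33% loss (about 117-121 per arm), 90% power is available for about 0.42-0.43 SD. Re-base the food-to-soothe calculation on the randomised arms as well. No numerical error is claimed there; it uses the same observational comparator.
- **6.2.1:** correct the sentence saying that 15 + 350 dyads are needed for the power calculations, and the 715 total.
- **Sections 2 and 6.5.1:** reconcile the EHL status of phase one before describing that group as unexposed.

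If the sponsor prefers to keep the phase-one contrast as primary, 15 dyads must be justified by a stated SD or a stated gain from adjustment.

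The cost is protocol wording and one recalculation, with no extra participants. The downside is that the comparison with the observational group, which section 2 wanted for generalisability, loses its primary status.

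### The 276 participants given for the primary endpoint cannot be traced to the stated inputs without unstated choices, and the comparison it is tied to is not the one the current design can support

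*Protocol*

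**What the plan says.** Section 6.6.2 contains the only power statement for the primary endpoint. It opens: "We have powered the study to detect a 0.67 difference in weight-for-age z-scores between the observational and future intervention groups". It continues: "To detect this difference with 90% power and a 5% Type I error rate, 276 participants are required", and adds: "This includes an anticipated 30% loss to dropout".

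The same paragraph then gives a second calculation, for use of food to soothe, which does state a variance and a retention rate ("assume a constant variance of 1 and a retention rate of 67% during the study period") and arrives at 300 pediatric participants. It closes with past experience: "We have experienced a 31-33% drop-out rate in previous studies of mother/guardian-infant dyads for longer than 3 months duration", and says similar drop-out is assumed here.

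Section 6.1 fixes 1:1 allocation, but only for the randomised phase. Section 6.2.1 plans 15 dyads in the observational phase and 350 in the randomised phase, and gives a total of about 715 subjects. The Primary Endpoints text also sets the observational phase against the treatment group.

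**The concern.** A sample size statement should let the reader recover the number from its inputs. Here the reader has the difference, power, error rate and loss, but not the SD, the number of sides, the ratio between the groups, or whether a participant is an infant or a member of a dyad. On the most natural assumptions the result is about half the printed figure.

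The statement also refers to a comparison with the observational group, which the plan keeps very small. A reader who takes the sentence at face value learns neither what the randomised comparison can detect nor how weak the named comparison is.

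**Working it through.** **Inputs from section 6.6.2:** difference 0.67, power 90%, Type I error 5%, loss 30%.

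**Inputs I had to assume:** two-sided test, equal groups, one z-score per infant, SD 1 with a range. A weight-for-age z-score is scaled to SD 1 in its reference population, which makes 1 the natural benchmark. The only variance in the section ("assume a constant variance of 1") belongs to the food-to-soothe calculation.

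**Attempt to reproduce 276.**

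Normal approximation, per group: n = 2 × (1.960 + 1.282)² × SD² / 0.67². At SD 1 this is 46.8, so 47 per group and 94 in all. Then 94 / 0.70 = 134.3, so 135 (136 if each group is rounded up).

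The two-sample t-test gives 47.8, so 48 per group and 96 in all. Then 96 / 0.70 = 137.1, so 138.

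| Assumed SD | Per group (t-test) | Evaluable | Recruited, 30% loss |
|---|---|---|---|
| 0.9 | 39 | 78 | 112 |
| 1.0 | 48 | 96 | 138 |
| 1.2 | 69 | 138 | 198 |
| 1.3 | 81 | 162 | 232 |

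A one-sided test at SD 1 gives 112. None of these is 276.

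**Unstated choices that do reach 276, or close to it.**

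- *Both dyad members counted:* 2 × 138 = 276.
- *Larger SD:* 276 × 0.70 / 2 = 96.6 per group. The standardised difference detectable at 90% power is 0.469, so the implied SD is 0.67 / 0.469 = 1.43.
- *Unequal groups at SD 1:* a 6:1 ratio needs 27.6 in the smaller group and 193.1 in all. Then 193.1 / 0.70 = 275.9 (280 once groups are rounded up).

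If 276 did mean infants split equally at SD 1 with 30% loss, power for 0.67 would be 99.6% rather than 90%.

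**The contrast named in 6.6.2, under the current plan.** The observational group has 15 dyads and the intervention arm has 350 / 2 = 175. At SD 1, two-sided t-test:

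- 15 versus 175: power about 70%.
- After 30% loss, 10.5 versus 122.5: power about 54%.

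**The randomised comparison, under the current plan.** With 33% loss, 350 × 0.67 = 234.5, or about 117 per arm. The standardised difference detectable at 90% power is 0.426. In z-score units:

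- SD 0.9: 0.426 × 0.9 = 0.38
- SD 1.0: 0.43
- SD 1.2: 0.426 × 1.2 = 0.51

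**Loss rate.** The section uses 30% for the z-score figure and 33% for food to soothe, and cites 31-33% from experience. With 96 evaluable, 31% gives 96 / 0.69 = 139.1, so 140; 33% gives 96 / 0.67 = 143.3, so 144. Against 138 the effect is small.

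**The case against.** The strongest reply is that nothing here shows 276 to be wrong. The section gives no SD for this calculation, so SD 1 is the reviewer's input. Section 6.1 states 1:1 only for the randomised phase, whereas the powered contrast crosses phases. The word used is participants, and the next calculation changes to pediatric participants, which fits a change of unit. Section 6.2.1's total of 715 equals 15 + 2 × 350, so randomised pairs are counted there as two subjects each. On that reading the arithmetic is sound and only the label is unclear.

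Most of this stands. A reader might infer a plain arithmetic error by a factor of exactly two, but the documents do not support that: the exact factor depends on SD 1 and on the t-test, since the normal approximation gives 135-136. Nor is an SD of 1.43 the only route to 276.

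A reader might also see a contradiction between 30% and 31-33%. The text says only that drop-out is assumed to be similar, and 30% is arguably that. The mismatch is untidy and nearly without effect.

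Finally, if 276 is too large it is conservative, and 350 dyads are planned. A null result would in any case be read from its confidence interval, so a claim that this sentence would mislead its interpretation goes too far.

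Two things survive. Counting mothers is the wrong unit for an endpoint with one value per infant, so that rescue leaves the statement needing correction. And no reading of 276 matches a contrast with only 15 observational dyads.

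**Conclusion.** The point holds as under-specification together with a mismatch to the design. The printed inputs alone do not determine 276. Under a two-sided t-test, equal groups and 30% loss they lead to about 138 infants at SD 1, and 112 to 198 for SDs of 0.9 to 1.2.

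The sentence does not give the power of either comparison the current plan can make. The named contrast has about 70% power at SD 1, or about 54% after 30% loss. The randomised contrast can detect about 0.43 z at 90% power with 33% loss (0.38 to 0.51 over the same SD range), which is well below 0.67.

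All of these rest on the assumed SD and on a simple comparison of two means; the mixed model in section 6.6.1 could do somewhat better. It might be inferred that the trial is too small or too large. The documents do not show that: for the randomised comparison, 350 dyads exceed the requirement at any SD in the range above.

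**What to change.** In section 6.6.2, replace the 276 sentence with a statement in dyads for the randomised comparison that gives the SD as an assumption, the sidedness, the 1:1 allocation and one loss rate used throughout (the 33% already used in the second calculation). For example: *with 350 dyads randomised 1:1 and 33% loss (about 117 per arm), a two-sided 5% test has 90% power to detect a difference of about 0.43 in weight-for-age z-score if the SD is 1 (about 0.38 at SD 0.9 and 0.51 at SD 1.2).*

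Remove 276, or relabel it as 138 dyads if the sponsor confirms that SD and that counting unit. Bring the comparison named in the Primary Endpoints text into line, and if the observational contrast is kept, state its power with 15 dyads.

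The cost is protocol wording. Enrolment does not change.

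### The food-to-soothe sample size joins a share of mothers (15%) to a variance of 1 and gives no control rate or mean difference, so 300 recruits for 80% power does not follow from the stated inputs

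*Protocol*

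**What the plan says.** Section 6.6.2 (Statistical Power and Sample Size Considerations) gives a second power statement after the one for weight-for-age z-score. For food to soothe it "uses nominal power = 0.8 and alpha = 0.05". The effect is worded as "If we assume that we can change 15% of mothers in the future treatment group to reduce their use of food to soothe", and the comparison is made "as compared to mothers in the observational study". The remaining inputs and the result come together: "assume a constant variance of 1 and a retention rate of 67% during the study period, we will need to recruit 300 pediatric participants".

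The section states no share of mothers using food to soothe under usual care, no mean difference, no scale for the variance, no sidedness and no allocation ratio for this comparison.

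Three other places bear on it. Section 6.1 randomises 1:1 in phase 2. Section 6.2.1 plans 15 observational dyads and 350 randomised dyads. Section 6.6.1 treats survey subscales as parametric and lists feeding practices among the continuous secondary outcomes.

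**The concern.** The effect is a proportion of people. The variance is one that a raw proportion cannot have, since p(1 − p) never exceeds 0.25. A variance of 1 suits a standardised score, but the effect would then have to be a difference in means, and there is none. Nothing in the section links the two scales.

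The protocol makes an explicit power claim on this outcome and prints both inputs and result, so the inputs should lead to the result. If they do not, a reader cannot tell whether a null finding on food to soothe would be informative, or what size of effect the trial can detect. The outcome is secondary, so the primary endpoint is not affected by this point.

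**Working it through.** **Inputs from Section 6.6.2:** power 0.80, alpha 0.05, effect 15% of mothers, variance 1, retention 67%, 300 recruits. **Assumptions (not stated):** two-sided alpha, equal arms, and the control rate wherever one is needed. z-values: 1.960 + 0.842 = 2.802.

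**Retained sample.** 300 × 0.67 = 201, or 100.5 per arm. For the planned trial, 175 × 0.67 = 117.25 per arm.

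**Can 300 be reproduced?** Not from the printed inputs. Each reading below needs something added.

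*Reading A: a 15-point fall in a raw proportion.* The variance of 1 is ignored and binomial variance is used. With p̄ = (p1 + p2)/2, the number per arm is

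n = [1.960·√(2p̄(1 − p̄)) + 0.842·√(p1(1 − p1) + p2(1 − p2))]² / 0.15²

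and recruits = 2n/0.67.

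| Control → treated | n per arm | Recruits | Power, 300 recruits | Power, 350 recruits |
|---|---|---|---|---|
| 20% → 5% | 76 | 227 | 90% | 94% |
| 25% → 10% | 100 | 299 | 80% | 86% |
| 30% → 15% | 121 | 362 | 72% | 79% |
| 40% → 25% | 152 | 454 | 62% | 69% |
| 50% → 35% | 170 | 508 | 58% | 64% |
| 57.5% → 42.5% | 174 | 520 | 57% | 63% |
| 70% → 55% | 163 | 487 | 60% | 66% |
| 85% → 70% | 121 | 362 | 72% | 79% |
| 90% → 75% | 100 | 299 | 80% | 86% |
| 95% → 80% | 76 | 227 | 90% | 94% |

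So 300 is recovered at 25% → 10% and at 90% → 75%. Fewer are needed outside those rates and more between them.

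*Reading B: a latent normal scale with SD 1, with 15% of mothers moved across a threshold.* Here d = Φ⁻¹(p1) − Φ⁻¹(p1 − 0.15) and n = 2(2.802/d)². Control rate 40%: d = 0.421, n = 89, 266 recruits. 50%: d = 0.385, n = 106, 317 recruits. 60%: d = 0.379, n = 110, 329 recruits. 70%: d = 0.399, n = 99, 296 recruits.

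*Reading C: 15% taken as a mean difference of 0.15 with SD 1.* n = 2(2.802/0.15)² = 698 per arm, and 2 × 698/0.67 = 2,084 recruits (2,087 with the t distribution). Power with 300 recruits would be 18%.

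**Detectable difference on an SD-1 scale.** 2.802 × √(2/100.5) = 0.395, so 300 recruits (201 retained) detect about 0.40 SD with 80% power.

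**Comparator.** All of these assume equal arms. The comparator named in Section 6.6.2 is the observational group, which Section 6.2.1 sets at 15 dyads. At 67% retention that is 15 × 0.67 ≈ 10. Against 117.25 retained in the treatment arm, the detectable difference is 2.802 × √(1/10.05 + 1/117.25) = 0.92 SD.

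**The case against.** The strongest defence is that the section does not describe a yes/no outcome at all. It speaks of mothers reducing a behaviour, which is graded, and Section 6.6.1 treats survey subscales as parametric. A standardised score with variance 1 fits that plan. If 15% of mothers are then thought of as moved across a threshold on that scale (Reading B), the requirement lies around 300 for mid-range control rates, and the planned 350 dyads would be enough at every rate tried.

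This has force, and it limits what can be claimed. It shows that 300 may have come from a coherent calculation. It does not show that it did: the protocol states no latent scale and no control rate, and an unstated assumption that recovers the figure is itself a missing input. The equal arms it needs are not available against 15 observational dyads.

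Two stronger readings are tempting, and neither is supported. A reader might infer that the stated inputs require about 2,090 recruits, so that 300 is too small by a factor of seven. That holds only if 15% means 0.15 SD, which the text does not say and which sits badly with its wording about a share of mothers. A reader might also infer that the trial is underpowered for most plausible control rates. The documents give no rate for food to soothe, so none can be called plausible or implausible from them.

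It is also fair to say that the outcome is secondary and that planned randomised enrolment, at 350, is above 300.

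**Conclusion.** The point holds in this form: the inputs mix two scales and omit the control rate or mean difference, so 300 recruits and 80% power are not shown. It is not established that 300 is wrong.

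The size of the gap depends on the reading. It is about 225 to 520 recruits as a raw proportion (control rates 20% to 95%), about 265 to 330 on an unstated latent normal scale (control rates 40% to 70%), and about 2,090 only if 15% means 0.15 SD. As a raw proportion, 350 dyads give 63% to 79% power for control rates of about 30% to 85%, and more than 80% at or below 25% or at or above 90%.

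These figures rest on two-sided alpha, equal arms, 67% retention and assumed control rates. The equal-arms assumption fails for the comparator that the section names. This should be corrected, but it does not touch the primary endpoint.

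**What to change.** Replace the food-to-soothe sentence in Section 6.6.2 with one calculation on one scale, comparing the randomised treatment and control arms, and state the sidedness of alpha.

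- If the outcome is a mean score, which is consistent with Section 6.6.1: state that 300 recruits (201 retained at 67%) detect 0.40 SD with 80% power, and delete the 15%.
- If the outcome is a proportion: state the assumed control rate and its basis, delete the variance of 1, and restate the power that the planned 350 dyads give for a 15-point fall.

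The cost is wording only, with no change to enrolment or data collection. The downside is that the power stated may be less favourable than 80%.
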